2.6.4 Compliance

Quarterly quality assurance checks will be carried out by a member of the trial team to assess compliance with the above intervention delivery. The appointed researcher will be supplied with a checklist of the intervention and placebo procedures and each PI will be checked against this.

Any deviations noted from the outlined trial interventions will be monitored by the TMG and TSC. If required further training will be implemented to resolve any inconsistencies.

2.7 Blinding

2.7.1 Methods for ensuring blinding

Local Trial Management

At each participating centre, a suitably qualified member of the research team will collect the baseline data before randomisation, so this data will be blind. Once all baseline data has been collected the member of the research team will randomise the patient and be told the allocation to enable them to prepare the appropriate intervention. They will inform the PI who will deliver the appropriate intervention. The PI will take no part in the post-treatment data collection or analysis of the participant beyond reporting of SAEs as appropriate.

All participants will be blinded and not know their treatment allocation through masking of the treatment syringe to prevent them from seeing the contents.

All trial procedures will take place alongside a rigorous programme of quality control. The CI in conjunction with the TC will be responsible for ensuring adherence to the trial protocols at the trial sites.

The ATM treatment CRF will collect confirmation that allocated treatment was delivered but will not specify the treatment delivered. Where a treatment other than that allocated was received this should be noted on the CRF and the study coordinating team will contact the site for further details once the CRF has been received and processed in the study office.

When any hospital notes are updated relating to treatment or GP letters dictated, it should be recorded that an injection was delivered as per the random allocation assigned by the ATM study. The type of injection should not be recorded.

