2. TRIAL DESIGN

2.1 Trial summary and flow diagram

This will be a single blinded, multi-centre, randomised placebo controlled trial. The considered opinion of the Arthritis Research UK CSG Think Tank – which included representatives from rheumatology, podiatry, orthopaedics, physiotherapy, general practice and research – was that in the non-athletic population there is very limited evidence of the effectiveness of eccentric loading exercises, or indeed any other intervention, for this condition. It was the considered opinion of the Think Tank that there was no ‘standard treatment’ for the general population. Therefore, the

pivotal and crucial trial design which is likely to influence clinical practice should involve a placebo-arm.

[figure not shown]
All patients who are willing to proceed will be approached by a suitably qualified member of the research team who are responsible for completing consent procedures and baseline demographic data and functional outcomes using VISA-A and EQ-5D-5L **before randomisation**. The patient will be randomised using a centralised telephone randomisation service to either the intervention or the placebo injection, on a 1:1 basis, stratified by centre and presence of bilateral symptoms. **After randomisation**, the suitably qualified member of the research team will then prepare the allocated injection for the principal investigator who will administer the injection. The participant will not know the treatment allocation.

Two hundred and forty patients will be randomised in total, across six participating centres. The intervention delivery will be standardised through initial training and on-going quality assurance checks by an independent researcher. The participants will then attend routine clinical appointments, (typically two weeks post injection to assess for any adverse events and six months post injection to review treatment efficacy). The participants will also receive two postal follow up questionnaires, as part of research procedures, at three and six months following randomisation.

The local principal investigator and research team at each site cannot be blind to treatment as they will be delivering the interventions. None of these team members will have a role in the collection of participant data after randomisation or analysis, beyond reporting adverse events.

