2.2.2 Secondary objective

Secondary Objectives:

1) To quantify and draw inferences on observed differences in VISA-A status at three months after treatment.

2) To identify any differences in health related quality of life measurement between trial treatment groups at three and six months after treatment.

3) To determine the complication rate of platelet rich plasma injections at three and six months after treatment.

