2.3.2 Safety

- Adverse event data

At each postal questionnaire follow up participants will be asked if they have had any adverse events and how they were managed. Additionally, at each participating site, the Principal Investigator (PI) will be asked to comply with procedures for reporting SAEs to the Trial Coordinator within 24 hours of becoming aware of an event – in line with Warwick SOPs outlined in sections 4.1.1.

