There is an active debate pertaining to the treatment effect of needling trauma, or the trauma of injecting fluid directly into the tendon. Therefore, a true placebo arm would need to avoid these possible treatment effects. The group consensus was therefore not to administer the placebo injection intratendinously.

Post Injection:

The participant will not be aware which treatment they have received, but the PI administering the treatment will.

After both treatments all participants will receive the same post injection advice sheet. The post injection advice sheet will inform participants that they may have increased pain for 24-48 hours, after which period they can resume their normal activities as pain allows. It will also include advice on potential adverse events (e.g. infection and reddening of the skin) and what to do if they occur.

In the case of participants with bilateral presentations, the index tendon will be randomised and managed accordingly. Regarding the non-index tendon the participant will have two options, to have no treatment or to receive a second injection into the non-index tendon.

All participants will then be followed up at standard clinical follow up appointments. These usually occur on two further occasions at two weeks after the injection and six months. The appointment at two weeks will allow the PI to check for the occurrence of any early complications (e.g. infection). The appointment at six months will allow the PI to assess the outcome from a clinical perspective and discuss with the participant at this point if any further clinical management is required.

Research follow up will be by postal questionnaire and will take place at three and six months after randomisation.

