3. METHODS AND ASSESSMENTS

3.1 Schedule of delivery of intervention and data collection

Visit Window (No. Weeks \pm No. Days)	Baseline	2 wk post randomisation	3 m (\pm 1 m) after randomisation	6 m (\pm 1m) after randomisation
Written informed consent	✓			
Baseline data	✓			
Randomisation	✓			
Intervention	✓			
CRF completion	✓	✓		✓
Questionnaires	✓		✓	✓
Adverse events	✓	✓	✓	✓

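### The protocol gives conflicting rules on whether the unblinded PI records non-serious adverse events, so early complications are likely to be recorded inconsistently by staff who know the arm

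*Protocol*

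**What the plan says.** The protocol describes the site team's safety-recording role in several places.

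- Section 2.7.1, on the PI: "The PI will take no part in the post-treatment data collection or analysis of the participant beyond reporting of SAEs as appropriate".
- Section 2.3.2 names one reporting duty for the PI, which is to notify SAEs to the Trial Coordinator within 24 hours.
- Section 2.1, on the PI and the site research team together: "None of these team members will have a role in the collection of participant data after randomisation or analysis, beyond reporting adverse events". The same section describes the purpose of the first clinic appointment as "typically two weeks post injection to assess for any adverse events".
- Section 2.6.3: "The appointment at two weeks will allow the PI to check for the occurrence of any early complications (e.g. infection").
- Section 3.1: the column headed "2 wk post randomisation" has ticks for CRF completion and for adverse events, and none for questionnaires.
- Section 4.1.1 requires all adverse events to go on a CRF. Expected events, such as infection, swelling and bleeding at the injection site, are exempt from 24-hour reporting but still go on the CRF. No recorder is named.

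On blinding, section 2.1 states: "The local principal investigator and research team at each site cannot be blind to treatment as they will be delivering the interventions". The participant's own route for reporting is in section 2.3.2: "At each postal questionnaire follow up participants will be asked if they have had any adverse events and how they were managed". The objective served by these data is the third in section 2.2.2: "To determine the complication rate of platelet rich plasma injections at three and six months after treatment".

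**The concern.** Sections 2.7.1 and 2.1 set different limits for the same person. One stops at serious events; the other covers adverse events of any grade. A PI who sees a minor local infection or skin reaction at two weeks is told by one section to stay out of data collection and by the others to check for it, at a visit where a form is due. Sites may settle this differently, and the count of non-serious complications would then depend partly on which sentence a site followed.

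Whichever way a site settles it, nobody blinded is assigned to the two-week assessment. The injector knows whether the tendon was penetrated five times with about 3 ml of PRP or a needle was placed under the skin with nothing injected (section 2.6.3). Minor complications involve judgement, and without a fixed set of questions the threshold for writing one down can shift with knowledge of the arm.

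At stake are secondary objective 3, the plots of complications over time and the possible Kaplan-Meier analysis in section 6.2, which names infection as an important class, and the safety data that the DMC reviews under section 7.9.

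**Working it through.** No figure in the protocol bears on this point, so the check is a comparison of sections.

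**1. What may the PI record after treatment?**

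| Protocol section | Who | What is allowed or required |
|---|---|---|
| 2.7.1 | PI | SAEs only |
| 2.3.2 | PI | SAEs within 24 hours; non-serious events not mentioned |
| 2.1 | PI and site team | Adverse events, no restriction to serious |
| 2.6.3 | PI | Check for early complications at two weeks |
| 3.1 | Not stated | Adverse events and CRF both ticked at two weeks |
| 4.1.1 | Not stated | All adverse events on a CRF, expected ones included |

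The first row cannot be squared with the third. Section 2.3.2 fits either rule, since it is silent on non-serious events.

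**2. Which reading was intended?** Sections 2.1, 2.6.3, 3.1 and 4.1.1 all point towards recording non-serious events at two weeks. Section 2.7.1 stands against them, and it restricts only the PI. Under section 2.1 another member of the site team could complete the form. The intended reading is therefore that these events are recorded at two weeks.

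**3. Does the intended reading remove the problem?** Not entirely. Section 2.1 describes the site research team, as well as the PI, as unable to be blind, and section 2.7.2 confirms that the team delivering the injection knows the allocation. Moving the task from the PI to a colleague in that team does not make the record blinded. The protocol text does not require the same questions to be put to every participant in both arms.

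**4. When does a blinded source first appear?** Participants are asked about adverse events with the follow-up questionnaires. The first is at three months with a window of one month either side, so it falls between 3 − 1 = 2 and 3 + 1 = 4 months after randomisation. The injection is in the baseline column of the schedule. A short-lived event in the first fortnight is then reported from memory. The two-week visit is the only scheduled assessment close to the injection.

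**5. Are the relevant events caught by the SAE route instead?** Mostly not. The events listed in section 4.1.1 as expected are taken out of 24-hour reporting and left to the CRF. Routine CRF entry is the kind of data collection that section 2.7.1 tells the PI to avoid.

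**6. Which arms does the objective cover?** Objective 3 speaks of PRP injections alone, while section 2.3 says that complications of the trial groups will be reported. Both arms have blood drawn, lignocaine and a needle, so events such as venesection bruising or fainting can be interpreted only against the placebo arm. Section 2.3 already provides for that; the wording of the objective lags behind it.

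**The case against.** The strongest reply is that this is one loosely worded sentence in a blinding section, outweighed by four other places. A reader might infer from section 2.7.1 that early non-serious complications go unrecorded until the three-month questionnaire. The documents do not support that: the schedule and section 4.1.1 call for recording at two weeks, and section 2.7.1 does not bind the rest of the site team. That part of the reply stands.

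The second reply is that unblinded site reporting is openly declared. The trial is described as single blinded, and section 2.1 names adverse event reporting as the exception. Moreover, objective 3 is set at three and six months, when blinded participants are asked directly. This also stands in large part. A reader might conclude that no fair comparison of complications between the arms is possible, but a blinded source exists at the times the objective names. Its weakness is recall of early events, and the declared exception does not explain why section 2.7.1 states a narrower one.

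Third, a reader might infer from objective 3 that complications will be counted in the PRP arm only. Section 2.3 says otherwise, and adverse events are collected from all participants.

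Finally, the choice of source for each complication table can be left to an analysis plan that is not shown here. That is fair for the tabulation. It does not extend to who records events at the visit, which sites take from the protocol and which an analysis plan cannot repair afterwards.

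**Conclusion.** The contradiction is real and needs reconciling. Its likely effect is inconsistent, unstructured recording of non-serious early complications by staff who know the allocation, rather than total loss of those events.

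The effect is confined to secondary objective 3 and the safety summaries that use the same data. The primary VISA-A comparison does not depend on it. No numerical size can be given: the protocol states no expected complication rate and nothing about how completely events would be recorded in either arm, so any risk ratio would merely restate the rates assumed. The direction of any bias is not fixed by the documents either.

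The conclusion assumes that sites could follow either sentence as written, that no CRF or working instruction outside the protocol already settles the matter, and that participants remain blinded when they report their own events. It is worth correcting before sites are trained, but it does not threaten the main result.

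**What to change.** 1. Reconcile sections 2.1, 2.3.2, 2.6.3, 2.7.1, 3.1 and 4.1.1 so that one named site role records all adverse events, including non-serious ones, at two weeks. State plainly that this person knows the allocation, if that is so.
2. Use one checklist of the events in section 4.1.1, put in identical form to every participant in both arms at that visit.
3. Ask the same items, with dates, in the existing three- and six-month questionnaires.
4. Tabulate complications by arm separately for blinded participant reports and for unblinded site-recorded events, and treat the participant reports as the fairer comparison between arms.
5. Reword objective 3 to cover complications in both trial groups, in line with section 2.3.

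The two-week CRF slot and the questionnaire item on adverse events already exist, so the cost is protocol wording and one checklist. The downsides are two sources to tabulate, which will not always agree, and participant reports of early events that rely on recall. The site record remains useful for timing, which is a reason to keep both.

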2.7.2 Methods for unblinding the trial

Code-break: is the term used for revealing treatment allocation. For ATM there will be a list of treatment allocations for all participants embedded in the database held at Warwick. The randomisation service is also provided by Warwick and the allocation data will be transferred internally from the randomisation service to the database, therefore allocation information will remain secure within Warwick.

Unblinding: The team delivering the injection treatment will be aware of the allocation. Unblinding of participants during the conduct of the trial is not allowed unless there are compelling medical or safety reasons to do so.

Emergency unblinding: The treatments in this study are considered low risk for the need for unblinding. However, if it is considered necessary to request unblinding after the treatment period the request should be directed to the CI via the 'ATM' central office, with full reasons for the request.

Unblinding after completion of the trial: The participants recruited to this trial may be invited to participate in longer term follow up and therefore may not be informed of their allocation at the end of the study. If follow up funding is not forthcoming within 12 months of the last participants 6 month follow up, participants will be informed by post, text or email of their treatment allocation if a request is made.

2.8 Concomitant illness and medication

2.8.1 Concomitant illness

Details of any concomitant illness will be recorded at trial entry and new illnesses recorded at follow up time points. If the change influences the participant's eligibility to continue in the trial, the CI will be informed.

2.8.2 Concomitant medication

Details of any concomitant medication will be recorded at trial entry. Any changes in concomitant medication will be recorded at each follow up questionnaire time point. If the change influences the participant's eligibility to continue in the trial, the CI will be informed.

2.9 End of trial

The trial will end when all participants have completed their six month follow-up.

The trial will be stopped prematurely if:

- Mandated by the Ethics Committee
- Following recommendations from the Data Monitoring Committee (DMC)
- Funding for the trial ceases

The Research Ethics Committee will be notified in writing if the trial has been concluded or terminated early.

3. METHODS AND ASSESSMENTS

3.1 Schedule of delivery of intervention and data collection

Visit Window (No. Weeks \pm No. Days)	Baseline	2 wk post randomisation	3 m (\pm 1 m) after randomisation	6 m (\pm 1m) after randomisation
Written informed consent	✓			
Baseline data	✓			
Randomisation	✓			
Intervention	✓			
CRF completion	✓	✓		✓
Questionnaires	✓		✓	✓
Adverse events	✓	✓	✓	✓

4. ADVERSE EVENT MANAGEMENT

4.1 Definitions

4.1.1 Adverse Event Management

An Adverse Event (AE) is defined as any untoward medical occurrence in a participant which does not necessarily have a causal relationship with this treatment/intervention. All AEs will be listed on the appropriate Case Report Form for routine return to the 'ATM' central office.

A Serious Adverse Event is an AE that fulfils one or more of the following criteria:

- Results in death
- Is immediately life-threatening
- Requires hospitalisation or prolongation of existing hospitalisation
- Results in persistent or significant disability or incapacity
- Is a congenital abnormality or birth defect
- Is an important medical condition.

All serious adverse events (SAE) will be entered onto the Serious Adverse Event reporting form and faxed to a dedicated fax machine at WCTU within 24 hours of the investigator becoming aware of them. Once received, causality and expectedness will be confirmed by the CI. SAEs that are deemed to be both unexpected and probably or definitely related to the trial will be notified to the Research Ethics Committee (REC) and sponsor within 15 days. All such events will be reported to the Trial Steering Committee and Data Monitoring Committee at their next meetings.

SAEs that may be expected as part of the injection interventions, and that do not need to be reported to the trial coordinating centre are: bruising and discomfort at the venesection site, syncopal (fainting) episode associated with venesection or tendon injection, infection, mild discomfort and bleeding at the injection site, swelling, skin discolouration and possible allergic reaction. Expected adverse events as detailed above will be recorded on the participants' CRF but do not have to be reported to the trial coordinating centre within 24 hours. All participants experiencing SAEs will be followed-up as per protocol until the end of the trial.

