The stratified randomisation procedure will ensure a balance in recruiting centres between test treatments. In addition to the unadjusted analysis (t-tests) we will also undertake regression analyses to adjust for any imbalance between test treatment groups in patient age or gender. The fixed effects analysis (linear regression model) will also be generalized by adding a random effect for recruiting centre to allow for possible heterogeneity in patient outcomes due more generally to the recruiting centre. VISA-A data will be assumed to be normally distributed during modelling, but subsidiary analyses may also be undertaken after appropriate variance-stabilizing transformation. The primary focus will be the comparison of the two treatment groups of patients, and this will be reflected in the analysis which will be reported together with appropriate diagnostic plots that check the underlying model assumptions. Treatment effects will be presented, with appropriate 95% confidence intervals, for both the unadjusted and adjusted analyses.

Temporal patterns of any complications will be presented graphically and if appropriate a time-to-event analysis (Kaplan-Meier survival analysis) will be used to assess the overall risk and risk within individual classes of important complications (e.g. infection). The decision about whether to undertake a time-to-event analysis will be data dependent; that is it will be dependent on the number of complications reported by study participants. The independent Data Monitoring and Ethics Committee will advise on this and suggest appropriate modifications to the statistical analysis plan as data is accumulated.

From the pilot data two patients from a sample of twenty presented with bilateral Achilles tendinopathy. For the full trial this small group will be randomised and treated as one unit i.e. the patient will be randomised rather than the tendon. Therefore, study participants presenting with bilateral tendinopathy will receive the same treatment on both sides. One side will be randomly selected, and designated as the index Achilles tendon. For those outcome measures (complications) that are side specific, we will use data from the index side only in the analysis. Randomisation will ensure approximate balance in bilaterals between groups; however, bilaterality will also be adjusted for in the definitive analysis. This will be incorporated into the Statistical Analysis Plan.

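### Section 4.1.1 gives three incompatible rules for a listed expected event that is serious: report within 24 hours, later by CRF, or not at all

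*Protocol*

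**What the plan says.** Protocol section 4.1.1 defines an SAE by the usual criteria, among them hospitalisation. It then sets a general rule: "All serious adverse events (SAE) will be entered onto the Serious Adverse Event reporting form". The form must reach WCTU by fax no later than 24 hours after the investigator learns of the event. After receipt, the chief investigator confirms causality and expectedness. Section 2.3.2 places the same duty on each site's principal investigator, who "will be asked to comply with procedures for reporting SAEs to the Trial Coordinator within 24 hours of becoming aware of an event". Neither statement carries an exception.

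The last paragraph of section 4.1.1 introduces a list of "SAEs that may be expected as part of the injection interventions, and that do not need to be reported to the trial coordinating centre". Besides minor venesection effects and fainting, the list names "infection, mild discomfort and bleeding at the injection site, swelling, skin discolouration and possible allergic reaction". The sentence after it refers back to the same items, now as expected adverse events. It says that they are recorded on the CRF and "do not have to be reported to the trial coordinating centre within 24 hours".

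The section also opens by having every adverse event listed on a CRF that is returned routinely to the central office.

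**The concern.** One event can fall under rules that cannot all be obeyed. The exempt list is headed as SAEs, so a site cannot safely assume that it covers only non-serious events. Read as written, the exemption reaches an infection that leads to admission or an allergic reaction that is serious.

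What is at stake is expedited review. Central confirmation of causality and expectedness starts when the SAE form arrives. If a listed event never generates a form, that step has no trigger, and the decision that the event was expected is in effect made at the site by matching it to a list. The investigator there gave the injection and knows the allocation (sections 2.1 and 2.6.3). A severe form of a listed event might well be judged unexpected, but nobody would be asked to judge it.

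**Working it through.** No sample size, power or event figure is involved, so the check is textual, with some simple timing.

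**1. The rules side by side**

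| Rule | Where | Label used | Report to WCTU? | When? |
|---|---|---|---|---|
| (a) | 4.1.1, general rule; deadline repeated in 2.3.2 | SAE | Yes, on the SAE form | 24 hours |
| (b) | 4.1.1, heading of the list | SAE | No | No time qualifier |
| (c) | 4.1.1, next sentence | Adverse event | By CRF | 24-hour deadline lifted |

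Rule (a) contradicts both (b) and (c). Rule (b) also contradicts (c) and the opening statement that all adverse events come in by CRF.

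**2. A test case.** Take an infection at the injection site that requires hospitalisation. It meets a seriousness criterion, so (a) applies. It is on the list, so (b) and (c) apply too. The three answers are 24 hours, never, and with the routine CRF. Bruising or mild discomfort would seldom be serious, so the conflict matters mainly for infection and allergic reaction.

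**3. Delay under (c).** Section 3.1 schedules CRF completion at baseline, two weeks, and six months ± 1 month. Assume that CRFs are completed only at those points, and that the event occurs just after the two-week visit (about 0.5 month).
- Next CRF, early end of window: 5 − 0.5 = 4.5 months later.
- Next CRF, late end of window: 7 − 0.5 = 6.5 months later.
- Three-month questionnaire (± 1 month), participant's own report: 2 − 0.5 = 1.5 to 4 − 0.5 = 3.5 months later.

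This is close to the longest wait. An event before or at the two-week visit would be picked up there.

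**4. Timing of committee review.** Section 7.9 has the DMC meet after 50% recruitment, which is 240 × 0.5 = 120 patients. The section 7.5 timetable passes that figure in month 26 (117.6 in month 25, 126 in month 26), with recruitment starting in month 9. That is 26 − 9 = 17 months, during which the SAE form is the one stated route for getting a serious event to WCTU promptly.

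**The case against.** The best defence is that the heading of the list contains a slip. Most of the items are minor, and the next sentence calls them adverse events. The phrase locating events at the injection site can be read as qualifying infection as well. On that view the authors meant only that expected non-serious events need no expedited report. This is plausible, and it supports the wording proposed below. It does not remove the problem, because the text says SAEs and neither infection nor allergic reaction carries an explicit severity limit.

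The defence does succeed against several stronger conclusions that a reader might draw:

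- **That serious infections go unreported.** This needs rule (b) read alone, against the sentence that follows it. All adverse events are returned by CRF, each questionnaire asks about them (section 2.3.2), and the two-week visit looks for early complications such as infection (section 2.6.3). The section as a whole supports delay, not loss of data.
- **That such events are kept from the DMC.** Section 7.9 gives the DMC safety data, not only SAE forms. The safety stopping rules are left for the committee to agree, and their content is not in the protocol.
- **That complications are under-counted in the PRP arm.** The exemption is the same in both arms, and both have venesection, lignocaine and a needle (section 2.6.3). Only the PRP arm has material injected into the tendon, but that does not make the reporting rule one-sided.
- **That the list exempts the main serious harms of PRP.** The protocol does not rank harms. Section 6.2 gives infection as an example of an important complication and says nothing similar of allergic reaction.

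**Conclusion.** The contradiction is real and lies in a rule that the protocol itself fixes, so it cannot be left to a statistical analysis plan. For a listed event that meets a seriousness criterion, sections 2.3.2 and 4.1.1 give three answers: report within 24 hours, report later by CRF, or do not report.

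On the mildest workable reading, (c), the data are kept. The event nevertheless misses the 24-hour SAE form and the chief investigator's check of causality and expectedness. The delay could reach about 4.5 to 6.5 months by CRF, assuming that CRFs are completed only at the scheduled points; a participant's questionnaire may shorten it. The number of events affected cannot be stated, since the protocol gives no rates of serious infection or allergic reaction. The primary VISA-A comparison is unaffected. Lost data, concealment from the DMC and bias between arms are not shown.

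**What to change.** Reconcile sections 2.3.2 and 4.1.1 with three changes of wording:

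1. At the head of the list, replace the term SAEs with *non-serious adverse events*.
2. Delete the unqualified statement that listed events need not reach the coordinating centre, and keep the instruction to record them on the CRF.
3. Add that any event meeting a seriousness criterion goes on the SAE form to WCTU within 24 hours, whether or not it is on the list.

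This is enough to resolve the conflict. Changing how expectedness governs onward notification to the ethics committee, sponsor or oversight committees is a separate question that need not be opened here. The cost is an amendment to the protocol wording, matching text in any SAE form guidance, and a few extra SAE forms.
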